8.4. Events or Outcomes Qualifying as AEs or SAEs

8.4.1. Clinical laboratory parameters

Abnormal laboratory findings (e.g., clinical chemistry, hematology) or other abnormal assessments (e.g. vital signs) that are judged by the investigator as **clinically significant** will be recorded as AEs or SAEs if they meet the definitions of sections 8.1.1.. Clinically significant abnormal laboratory findings or other abnormal assessments that are detected during the study or are present at informed consent and significantly worsen during the study will be reported as AEs or SAEs. Clinically significant abnormal laboratory findings or other abnormal assessments that are associated with the disease being studied and are present at the start of the study but do not worsen, will **not** be reported as AEs or SAEs. However, if these findings or assessments are judged by the investigator to be more severe than expected considering the patient's condition, then they may be reported as AEs or SAEs.

8.4.2. Pregnancy report

Patients who become pregnant at any time will be immediately withdrawn from participation in the study. All appropriate withdrawal assessments may be performed at the discretion of the investigator.

The investigator will collect pregnancy information on any woman patient or partner of a male patient, who becomes pregnant and their partner while participating in this study. The investigator will record pregnancy information on a specific pregnancy notification form and submit it to ABIVAX or its designee within 24 hours after knowledge of a patient's or partner's pregnancy. The patient or partner will also be followed to determine the outcome of the pregnancy, be it full-term or prematurely terminated. Information on the status of the mother and child will be forwarded to ABIVAX or its designee. Follow-up will normally end 6 to 8 Weeks following the estimated delivery date.

While pregnancy itself is not considered to be an AE or SAE, any pregnancy complication or elective termination of a pregnancy for medical reasons will be recorded as an SAE. A spontaneous abortion is always considered to be an SAE and will be reported as such.

The time period for collecting pregnancy information is identical to the time period for collecting AEs, as stated in Section 8.5, Time Period, Frequency, and Method of Detecting AEs and SAEs. Pregnancy information is collected from the signing of informed consent to 4 Weeks after the last dose.

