- Females and males receiving the study treatment (potentially in combination with immunosuppressant) and their partners must agree to use a highly effective contraceptive method during the study and for 6 months after end of study or early termination. Contraception should be in place at least 2 Weeks prior to study participation. Women must be surgically sterile or if of childbearing potential must use a highly effective contraceptive method. Women of childbearing potential (WOCBP) will enter the study after confirmed menstrual period and a negative pregnancy test. Highly effective methods of contraception include true abstinence, intrauterine device (IUD) or hormonal contraception aiming at inhibition of ovulation, intrauterine hormone releasing system, bilateral tubal ligation, vasectomized partner. True abstinence is defined when this is in line with the preferred and usual lifestyle of the patient. In each case of delayed menstrual period (over one month between menstruations) confirmation of absence of pregnancy is required. This recommendation also applies to WOCBP with an infrequent or irregular menstrual cycle. Female and male patients must not be planning pregnancy during the trial and for 6 months post completion of their participation in the trial. In addition, male participants should use condoms and not donate sperm as long as contraception is required.

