8.5. Time Period, and Frequency of Detecting AEs and SAEs

All AEs and SAEs occurring from the time a patient consents to participate in the study until 4 Weeks after he or she has completed or discontinued the investigational medicinal product must be recorded in the Patient's eCRF.

Moreover, any occurrence of pregnancy within 3 months post stopping dosing must be reported.

Importantly, SAEs will have to be reported, either by email or by Fax, to IntuVigilance Limited within 24 hours of awareness of an SAE.

IntuVigilance Limited

[name]
Hotline phone: [REDACTED]

Email Address: [REDACTED]

Fax number: [REDACTED]

Legislative guidance requires the investigator to also ensure that any **related** SAEs are reported after the patient finished the study if the investigator becomes aware of them.

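### Protocol 8.4.2 stops collecting pregnancy information 4 weeks after the last dose, while 8.5 makes pregnancies reportable for 3 months

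*Protocol*

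**What the plan says.** Section 8.4.2 of the protocol (Pregnancy report) sets out how pregnancies are handled. The investigator collects information on any female patient, or partner of a male patient, "who becomes pregnant and their partner while participating in this study". The investigator records it on a dedicated form and must "submit it to ABIVAX or its designee within 24 hours after knowledge" of the pregnancy. The outcome is then followed: "Follow-up will normally end 6 to 8 Weeks following the estimated delivery date".

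The section ends with two sentences on timing. The first ties the window to adverse events: "The time period for collecting pregnancy information is identical to the time period for collecting AEs, as stated in Section 8.5". The second gives the limits: "Pregnancy information is collected from the signing of informed consent to 4 Weeks after the last dose".

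Section 8.5 sets the adverse event window as running from consent "until 4 Weeks after he or she has completed or discontinued the investigational medicinal product". Its next paragraph adds that "any occurrence of pregnancy within 3 months post stopping dosing must be reported".

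Section 4.2.1 sets a third, longer period, for contraception only. It binds patients and partners alike, who "must agree to use a highly effective contraceptive method during the study and for 6 months after end of study or early termination".

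**The concern.** Two adjacent sections give different post-treatment limits for pregnancy: 4 weeks and 3 months. The 4-week limit in 8.4.2 does match the adverse event window it cites. What it leaves out is the separate pregnancy duty in the following paragraph of 8.5.

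The section titled as the pregnancy procedure is where a site will naturally look, and it gives an explicit end date. A site that relies on it could fail to report a pregnancy in weeks 5 to 13. Alternatively, it could report the pregnancy without the form and without following the outcome.

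The outcome matters because 8.4.2 treats every spontaneous abortion as an SAE, whereas after 4 weeks 8.5 asks only for SAEs considered related. In the gap, pregnancy follow-up is the main route by which such outcomes would be captured. Section 1.2.5.1 reports that no-effect levels for embryo-fetal development in rabbits and for pup development in rats were below stated doses (redacted), so these data are of real interest.

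**Working it through.** There is no sample-size, power or alpha figure to reproduce. The check is a comparison of text plus calendar arithmetic.

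**Inputs**

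| Item | Source | Value |
|---|---|---|
| Pregnancy information collection | Protocol 8.4.2 | to 4 weeks after last dose = 28 days |
| AE/SAE recording | Protocol 8.5 | to 4 weeks after study drug = 28 days |
| Pregnancy reporting | Protocol 8.5 | to 3 months after stopping = 90 to 92 days |
| Contraception | Protocol 4.2.1 | 6 months after end of study or early termination = about 181 to 184 days |
| Last scheduled pregnancy test, completers | Protocol Table 1 and 5.2.5 | 3 weeks after Day 120 |
| Last scheduled pregnancy test, early discontinuers | Protocol 5.2.5 | 3 weeks after last dose |

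**Step 1: length of the gap.** Gap = (3 months in days) − 28.

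- 90 − 28 = 62 days (day 29 to day 90), 62/7 = 8.9 weeks
- 91 − 28 = 63 days (day 29 to day 91), 63/7 = 9.0 weeks
- 92 − 28 = 64 days (day 29 to day 92), 64/7 = 9.1 weeks

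**Step 2: does contraception cover the gap?** Counted at the earliest from the last dose, the 6 months end at day 181 to 184. Both exceed 92, so the requirement covers the whole gap.

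**Step 3: would scheduled testing find these pregnancies?** For completers not entering the extension, the last test is at 120 + 21 = Day 141, and 141 − 113 = 28 days after Day 113. For early discontinuers it is about 21 days after the last dose. No partner testing is scheduled. By the nominal schedule no test falls inside the gap, so a pregnancy there becomes known only if the patient or partner tells the site.

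**Step 4: which procedures apply in the gap?**

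| Element | 8.4.2 | 8.5 |
|---|---|---|
| Duty after 4 weeks | window closed | must be reported, to 3 months |
| Form | pregnancy notification form | none named |
| Deadline | 24 hours from knowledge | 24 hours for SAEs only; 8.4.2 says pregnancy itself is not an AE or SAE |
| Outcome follow-up | to 6–8 weeks after due date | none stated |

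The 24-hour and follow-up sentences in 8.4.2 carry no cut-off of their own. However, the sentence that creates the collection duty is limited to pregnancies during study participation, and the section closes with the 4-week limit. Whether the procedures reach a pregnancy at, say, week 8 after the last dose cannot be settled from the text.

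**The case against.** The strongest reply is that the sections do not contradict each other. Section 8.5 introduces the 3-month rule as an addition, nothing in 8.4.2 permits silence after 4 weeks, and a site can obey both by collecting to 4 weeks and reporting to 3 months. Section 8.4.2 also sends the reader to 8.5, the very next section. Because the form and the 24-hour deadline are triggered by knowledge of a pregnancy, and the protocol describes no other route, the natural reading is that they apply to late reports too. Four weeks also coincides with the last scheduled pregnancy test for completers, which could explain a shorter collection period. Finally, the 9 weeks is a calendar difference, not demonstrated harm.

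Much of this stands. The longer duty exists and is findable, events should be rare, and no effect can be counted. The pregnancy form and site instructions are not among the documents, so they may already say 3 months.

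It does not remove the problem. On the collect-then-report reading, a pregnancy in weeks 5 to 13 must be reported but its information need not be collected, which leaves outcome data unassured. The protocol does not state the testing-based rationale. Section 8.4.2 presents 4 weeks as the pregnancy window itself and cites 8.5 as its source while omitting the rule there that is specific to pregnancy.

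**Conclusion.** The inconsistency is real and should be corrected. For 62 to 64 days after the 4-week limit (day 29 to day 90–92 after the last dose), 8.5 requires pregnancies to be reported while 8.4.2 has closed collection, and the procedures that would capture the outcome are not clearly in force.

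The size rests on taking 3 months as 90 to 92 days and on treating the last dose in 8.4.2 and the end of dosing in 8.5 as the same date. The point applies only to patients who do not roll over into ABX464-104 and to partners of such male patients. The 6-month contraception requirement covers the whole interval and limits the expected number of events. The documents give no basis for estimating that number. Efficacy endpoints, analyses and sample size are not affected.

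**What to change.** Replace the last two sentences of Section 8.4.2 with wording to this effect:

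> The window for pregnancy information opens at consent and closes 3 months after the last dose, as Section 8.5 requires. The notification form, 24-hour submission and outcome follow-up apply throughout this window, including after the patient has left the study.

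Any site instructions that repeat the 4-week limit should be brought into line.

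The cost is two sentences in the protocol and any matching line in site materials. Section 10.1.2 provides for amendments to go to the IRB or IEC, so the change is best carried in the next amendment. It adds no visits or tests, and the 3-month duty is one the sponsor has already set.

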8.5. Time Period, and Frequency of Detecting AEs and SAEs

All AEs and SAEs occurring from the time a patient consents to participate in the study until 4 Weeks after he or she has completed or discontinued the investigational medicinal product must be recorded in the Patient's eCRF.

Moreover, any occurrence of pregnancy within 3 months post stopping dosing must be reported.

Importantly, SAEs will have to be reported, either by email or by Fax, to IntuVigilance Limited within 24 hours of awareness of an SAE.

IntuVigilance Limited

[name]
Hotline phone: [REDACTED]

Email Address: [REDACTED]

Fax number: [REDACTED]

Legislative guidance requires the investigator to also ensure that any **related** SAEs are reported after the patient finished the study if the investigator becomes aware of them.

8.6. Recording AEs and SAEs

Severity of AEs will be assessed according to CTC-AE Classification Version 5.0.

Patients will be asked to report all AEs as part of the procedures performed at each study visit. The site personnel will document all AEs in the patient's medical record. All AEs subsequently must be recorded in the appropriate eCRF sections.

The following points must be recorded for each event:

- A description of the event in medical terms, not as reported by the patient;
- Date of onset (start date);
- Date of resolution (stop date);
- The time of onset with respect to administering the investigational medicinal product;
- The severity of the sign/symptom or clinically significant abnormal laboratory value according to CTC-AE Classification (Version 5.0);
- The causal relationship between the investigational medicinal product and the occurrence of each AE. This will be assessed by each investigator using clinical judgment. Alternative causes, such as natural history of the underlying diseases, concomitant medications, other risk factors and the temporal relationship of the event to the investigational medicinal product will have to be considered. The causality of all AEs should be assessed by the investigator with the following question: Is there a reasonable possibility that the AE may have been caused by the investigational medicinal product? And answered "NO" (if not related) and "YES" (if related);
- Action taken regarding the investigational medicinal product:
 - No action;
 - Temporary discontinuation;
 - Permanent discontinuation;

- Recovered without sequelae / resolved without sequelae;
- Recovered with sequelae / resolved with sequelae;
- Recovering/Resolving;
- On-going;
- Fatal (for SAEs only).

- Patient's outcome.

If in any one patient, the same AE occurs on several occasions, the AE in question must be documented and assessed a new each time.

8.7. Reporting of SAEs to ABIVAX or its designee

Throughout the study, the reporting of SAEs to the Sponsor or its designee will be done through the SAE forms.

It is the investigator's responsibility to ensure that the SAE report is submitted to IntuVigilance Limited **within 24 hours after knowledge of the event(s)**.

The study specific SAE form should be completed as thoroughly as possible, with all the available details of the event and signed by the investigator or designee. The investigator will assess causality between the study drug and the adverse event (AE) / serious adverse event (SAE) according to the table outlined below:

Related	A clinical event, including laboratory test abnormality, occurs in a plausible time relationship to treatment administration, and which concurrent disease or other drugs or chemicals cannot explain.
Probably related	A clinical event, including laboratory test abnormality, with a reasonable time sequence to administration of the treatment, unlikely to be attributed to concurrent disease or other drugs or chemicals.
Possibly related	A clinical event, including laboratory test abnormality, with a reasonable time sequence to administration of the treatment, but which could also be explained by concurrent disease or other drugs or chemicals.
Unlikely to be related	A clinical event, including laboratory test abnormality, with a temporal relationship to treatment administration which makes a causal relationship improbable, and in which other drugs, chemicals or underlying disease provide plausible explanations.
Unrelated	A clinical event, including laboratory test abnormality, with little or no temporal relationship with treatment administration. Typically explained by extraneous factors (e.g., concomitant disease, environmental factors or other drugs or chemicals).

An assessment of causality should always be provided at the time of the initial report. If the investigator or designee does not have all information regarding the SAE, he/she should not wait to receive additional information before completing the form and notifying IntuVigilance Limited.

Additional or follow-up information relating to the initial SAE report, will be requested, if necessary. Again, this information is to be completed and submitted through the SAE forms within 24 hours of receipt of the information.

In the rare occasion when the facsimile equipment does not work or in the absence of facsimile, the investigator should notify IntuVigilance Limited by telephone within the given timeframe and send a copy of the SAE report form by email.

8.8. Reporting of SAEs to Regulatory Authorities

ABIVAX has a legal responsibility to notify, as appropriate, both the local regulatory authorities and other regulatory agencies about the safety of the investigational medicinal product. It is therefore important that the investigator notifies promptly (within 24 hours) ABIVAX or designee of any SAEs, in order for legal obligations and ethical responsibilities towards other patients to be met.

In addition, the investigator or designee, will comply with the local regulatory requirements (when applicable) in reporting of SAEs to the ethics committee and, if required, to the relevant government authority.

Safety reports on adverse events that are serious AND unexpected AND causally associated with the investigational medicinal product are prepared according to ABIVAX's policy and applicable regulations and are forwarded to the investigators. These reports are filed with the investigator brochure or other appropriate study documentation. It is the Sponsor or its designee and/or investigator's responsibility to notify the IRB or IEC of these reports, if applicable according to local requirements.

9. DATA ANALYSIS AND STATISTICAL CONSIDERATIONS

A summary of the principal features of the statistical analysis of the data will be described here, in the statistical section of the protocol. A more technical and detailed elaboration of the principal features stated in the protocol will be given in the first version of the statistical analysis plan (SAP).

Any amendments to the SAP will be clearly documented and signed prior to the final database lock including justifications and details of their potential impact on the interpretation of the study results.

9.1. Statistical and Analytical Plans

No interim analysis is planned.

The study analysis will be performed following database lock upon the completion of the last patient or upon its early discontinuation whichever occurs first.

9.1.1. Protocol deviations

Protocol deviations will be reviewed and classed as major or minor during the blind-review meeting. Major protocol deviations are defined as deviations liable to bias the evaluation of the main efficacy endpoint. The following deviations will be considered as major (non-exhaustive list):

- Non compliance with the inclusion or exclusion criteria;
- Non compliance with the study treatment;
- Intake of prohibited medication;
- Noncompliance with time window.

9.1.2. Definition of study analysis sets

The following datasets will be defined and used for the analyses:

- The **Safety dataset (SAF population)** is defined as those patients included in the study, who have received at least one dose of the study treatment.
- The **Full Analysis dataset (FAS population)** is defined as those patients included in the study, who have received at least one dose of the study treatment, and who have at least one baseline data.
- The **Per Protocol dataset (PP population)** is defined as those patients of the FAS population without any major protocol deviation.

9.1.3. Patients/Patients disposition

The number and the percentages of patients enrolled and included in each of the populations will be tabulated. The reason for patient exclusions from each of the populations will also be listed. In addition, the number of discontinued patients with their reason for discontinuation will be tabulated.

9.1.4. Demographic and other baseline characteristics

Demographics and other baseline characteristics will be summarized by treatment arm. This analysis will be conducted on the FAS population.

9.1.5. Treatment compliance

Number of daily doses will be presented on the FAS population.

9.2. Efficacy Analysis

Analysis of efficacy data will be carried out in the Full Analysis Set in which subjects who prematurely discontinue the study due to adverse reaction(s) will be considered treatment failures.

The primary efficacy endpoint of the study is the change in the Modified Mayo Score (MMS) from Baseline to Week 8. This change will be compared between subjects who received ABX464 and placebo for each ABX464 treatment arm separately using an ANCOVA model adjusting for randomized study treatment arm, previous biological or JAK inhibitors treatment use (i.e. randomization strata), and baseline MMS.

The dose testing will commence with comparing the ABX464 50mg dose with placebo. If this is significant at a 5% two-sided level (i.e. $p < 0.05$) a comparison against placebo will be carried out at the ABX464 100mg dose. Again, if significance at a 5% level for this test is observed the procedure will be repeated at the ABX464 25mg dose. In this closed procedure no adjustment for multiple comparison is needed. Should the data warrant it, testing between doses may also be conducted.

In addition, descriptive statistics will be presented by treatment arm for all secondary efficacy variables for each measurement timepoint.

These statistics include:

- Continuous variables: mean, standard deviation, minimum and maximum, 95%
- Confidence intervals for the mean, median and quartiles will be presented.
- Categorical variables: counts, rates and 95% confidence intervals for the rates will be calculated.

In addition to descriptive statistics, the following analyses will also be carried out for the variables indicated below:

- The global (combined) ABX464 treatment effect vs. placebo in the change from Baseline in Modified Mayo Score at Week 8
- The proportion of subjects with clinical remission at Week 8 will be compared across study treatment arms using a stratified Mantel-Haenszel test.
- Mixed model analysis of covariance will be conducted for the following measurements:
 - The change from baseline in microRNA-124 levels in total blood (PAXgene®) at Week 1, Week 4, Week 8 and Week 16 and in tissue (RNA later).
 - The change from baseline in fecal calprotectin levels at Week 8 and Week 16.
 - The change from screening in the histopathology/infiltrate (rectal/sigmoidal biopsies) assessed by the Robarts Histopathology Index, the Geboes and Nancy Histology Scoring Scales at Week 8 and Week 16 (if available).
 - The change from screening in Modified Mayo scores and Partial Mayo scores during the study.

In this mixed model, treatments and stratum will be fixed effects, subject will be random effect and baseline values of the respective measurements will be covariates. Other explanatory variables will also be allowed to be included in the model. To normalize eventual skewed distributions transformation of the data will also be considered. Study treatment groups will be compared within this model framework. All p-values will be interpreted in a descriptive manner.

The following subgroups will be analyzed:

- Gender
- Age
- Country
- US vs non-US
- Baseline MMS
- With/without previous biological or JAK inhibitors treatment
- Week 16 ABX464-NGlu AUC0-12 level above/below 7 000 h*ng/mL (vs. placebo)
- Concomitant UC medications.

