2.3. ESTIMANDS

The primary and secondary estimands to support regulatory decisions are described in Table A below. The intercurrent event is the early discontinuation of patients from the study and/or missing Week 8 efficacy assessments.

Table A List of Estimands

Document: \\ieddc-vnasc01\BIOSdata\Abivax\ABX464\FZA92720\Biostatistics\Documentation\SAP\ABX464-103_SAP_V2.0_10MAY2021

Author: [REDACTED]

Version Number: 2.0
Version Date: 10May2021

Template No.: CS_TP_BS016 Revision 5

Reference: CS_WI_BS005

Effective Date: 01Apr2018

Estimand	Definition	Attributes			
		Population	Variable/Endpoint	Intercurrent event handling strategy	Population-level summary measure
Primary	Optimal ABX464 dose	All patients randomized, received at least one dose of study drug and provided at least one efficacy data point	Mean change in MMS from baseline to Week 8	Missing Week 8 MMS components (stool frequency, rectal bleeding and endoscopy subscores) will be imputed using methods detailed in section 7.3.	Mean change from baseline
Secondary	The effect of different dose groups vs placebo on secondary variables	All patients randomized, received at least one dose of study drug and provided at least one efficacy data point	Mean change from baseline to Weeks 8 and 16 in pMMS	Missing Week 8 pMMS components (stool frequency and rectal bleeding subscores) will be imputed using methods detailed in section 7.3.	Mean change from baseline
			Clinical remission or response at Weeks 8 and 16	Patients with missing Week 8 assessment will be considered non-responders	Proportion of responders in each treatment group
			Mean change from baseline to Week 8 in fecal calprotectin and CRP levels	Missing fecal calprotectin and CRP values will not be imputed.	Mean change from baseline

Document: \\ieddc-vnasc01\BIOSdata\Abivax\ABX464\FZA92720\Biostatistics\Documentation\SAP\ABX464-103_SAP_V2.0_10MAY2021

Author: [REDACTED]

Version Number: 2.0
 Version Date: 10May2021

Template No.: CS_TP_BS016 Revision 5

Reference: CS_WI_BS005

Effective Date: 01Apr2018

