7.3. MISSING DATA

A subject's missing efficacy data viz. MMS (or any components of MMS missing) at Week 8, will be imputed and the subject will be considered as a non-responder for clinical remission and response.

Missing MMS components at Week 8 will be imputed as follows:

Stool Frequency Sub score: The average of the 3 recent eDiary stool frequency records (if no prior records then choose records after the Week 8 visit date) within 10 days of date of week 8 visit is calculated. The normal stool frequency (at screening) is subtracted from the average and rounded to a whole number. The imputed sub score will be assigned as follows:.

Sub score=0; if calculated value =0

Sub score=1; if calculated value=1,2

Sub score=2; if calculated value=3,4

Sub score=3; if calculated value=5 or greater

If no records available within 10 days from eDairy, the nearest neighbour method will be considered.

Rectal Bleeding Sub score: The worst of the 3 recent eDiary records within 10 days of Date of Week 8 visit, will be considered as the analysis value (if no prior records then choose records after the Week 8 visit date) . If no records available within 10 days from eDairy, the nearest neighbour method will be

Document: \\iedc-vnasc01\BIOSdata\Abivax\ABX464\FZA92720\Biostatistics\Documentation\SAP\ABX464-103_SAP_V2.0_10MAY2021

Author: [REDACTED]

Version Number:
Version Date:

2.0
10May2021

Template No.: CS_TP_BS016 Revision 5

Reference: CS_WI_BS005

Effective Date: 01Apr2018

considered.

Mucosal appearance at Endoscopy: The analysis value of the nearest neighbour is used to impute missing Endoscopy sub score. The nearest neighbour is defined as the subject in Placebo arm with non-missing sub score, matching the 'subject with missing value' by Gender, Baseline MMS, Age and Previous Exposure to other biologics/JAK status. The matching score is calculated for all the placebo subjects with non-missing sub score, as follows:

- 1) If the subject matches in gender, 5 points assigned.
- 2) If previous exposure status matches, then additional 5 points.
- 3) The absolute difference between the Baseline MMS and Age, is subtracted from the scores.

The Placebo subject with the highest score is considered the nearest neighbour. In case of tied nearest neighbour scores, the worst sub score value will be used to impute.

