15.1.2. MISSING DATA METHODS FOR PRIMARY EFFICACY VARIABLE

Subjects with missing primary efficacy values will be imputed as non-responders for clinical remission and response at Week 8. Missing MMS scores at Week 8 will be imputed as mentioned in section 7.3.

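### The protocol's treatment-failure rule for adverse-reaction discontinuers is not carried into the primary MMS change; the SAP uses placebo-derived values there, without declaring the departure or planning an analysis that would show its effect

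*Protocol*

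**What the plan says.** Protocol 9.2 places the efficacy analysis in the full analysis set and adds that "subjects who prematurely discontinue the study due to adverse reaction(s) will be considered treatment failures". The next sentence reads "The primary efficacy endpoint of the study is the change in the Modified Mayo Score (MMS) from Baseline to Week 8". The failure rule is not restricted to responder endpoints, and no MMS value is given for a failure. The statistical methods in the protocol synopsis omit the rule.

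SAP 2.3 treats all reasons for stopping alike: "The intercurrent event is the early discontinuation of patients from the study and/or missing Week 8 efficacy assessments". For the primary estimand, "Missing Week 8 MMS components (stool frequency, rectal bleeding and endoscopy subscores) will be imputed using methods detailed in section 7.3".

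SAP 7.3 then works by component:

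- **Stool frequency:** "The average of the 3 recent eDiary stool frequency records" within 10 days of the Week 8 visit, less the patient's normal frequency.
- **Rectal bleeding:** "The worst of the 3 recent eDiary records within 10 days of Date of Week 8 visit, will be considered as the analysis value".
- **Either symptom score with no diary record in the window:** the nearest-neighbour method.
- **Endoscopy:** always the nearest neighbour, in every arm. "The nearest neighbour is defined as the subject in Placebo arm with non-missing sub score", matched on gender, baseline MMS, age and previous biologic or JAK inhibitor exposure.

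Failure appears in the SAP only for the binary outcomes (7.3 and 15.1.2): "Subjects with missing primary efficacy values will be imputed as non-responders for clinical remission and response at Week 8". SAP 3.3, which lists changes from the protocol, does not mention the adverse-reaction rule. SAP 15.1.4 plans two sensitivity analyses of the primary endpoint, per protocol and subgroups.

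**The concern.** One patient can be a failure on remission and response and yet carry an improved value on the primary score. The protocol's sentence stands directly before the definition of the primary endpoint, so a reader would expect it to govern that endpoint or to be told that it does not.

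The primary objective is to find an optimal dose, and SAP 7.4 and 15.1.3 also plan comparisons between doses. How intolerance is scored can therefore bear on the dose conclusion if intolerance differs between arms. As planned, the report would not show whether it does. The per-protocol analysis excludes patients with no Week 8 MMS (SAP 5.2.4), so it removes these patients instead of scoring them as failures. The subgroup analyses repeat the same imputation.

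**Working it through.** **1. The plan's own figure.** Protocol 9.4 gives mean reductions of 2.5 (ABX464) and 1.0 (placebo), SD 2.1, two-sided 5%, power above 90%, a t-test, 5% dropout in all arms, and 58 per arm, later raised to 61.

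- Exactly 90% power for one comparison needs 43 evaluable per arm; 43/0.95 = 45.3, so 46.
- 58 x 0.95 = 55.1, so 55 evaluable. That gives 96.0% power per comparison and, by simulation with a shared placebo arm (100,000 runs), 90.7% for passing all three gate-kept tests.

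The stated 58 is thus consistent with the stated power, and the planning means can be used below.

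**2. Who is affected.** Only patients who stop for an adverse reaction before Week 8 and lack Week 8 MMS components. Anyone who stops later keeps the observed Week 8 score.

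**3. Where their values come from.** The End of Study list in Protocol 5.2.5 has partial MMS but no sigmoidoscopy, so endoscopy will normally be donor-based. The e-diary is kept from screening to end of study (Protocol 5.2.1). A patient who stops early has no Week 8 visit date to anchor the 10-day window, so the donor fallback is likely for symptoms too, but not certain. SAP 6.3 maps early-discontinuation data to the next visit, though only for by-visit summaries.

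**4. Expected effect under each rule.** Let da and dp be the active and placebo shares affected. Assume that failure is scored as zero change, that all components come from donors, and that recipients have on average the same baseline as donors.

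- Failure rule: 2.5(1 - da) - 1.0(1 - dp)
- Donor rule: [2.5(1 - da) + 1.0 da] - 1.0 = 1.5(1 - da)
- Donor minus failure: 1.0 x (da - dp)

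Between two active doses the same algebra gives 1.0 x the difference in their shares. The documents give no rates by arm, so the rates below are assumed. Power is simulated at 61 per arm (20,000 runs, normal data, randomly drawn placebo donors, t-test).

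| da / dp | Failure rule | Donor rule | Excess | Power, failure | Power, donor |
|---|---|---|---|---|---|
| 5% / 5% | 1.425 | 1.425 | 0 | 96% | 96% |
| 10% / 5% | 1.30 | 1.35 | 0.05 | 93% | 94% |
| 20% / 5% | 1.05 | 1.20 | 0.15 | 81% | 90% |
| 30% / 5% | 0.80 | 1.05 | 0.25 | 58% | 81% |

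Against the planned 1.5-point effect, 0.05 is 0.05/1.5 = 3% and 0.15 is 0.15/1.5 = 10%.

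**5. If only endoscopy is donor-based.** If endoscopy carries one third of the placebo gain (an assumption), the donor-supplied excess is one third of the above: about 0.02, 0.05 and 0.08 in the last three rows. The symptom part then depends on the patient's own diary.

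**6. No true effect.** With equal means in both arms, the same simulation rejected in favour of active under the donor rule in 2.4% of runs at 5/5%, 1.9% at 20/5% and 1.4% at 30/5%, against a nominal 2.5%.

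**The case against.** The strongest reply is that treatment failure is naturally a responder concept. The protocol gives it no MMS value, the synopsis omits it, and Protocol section 9 leaves technical detail to the SAP, which applies failure to remission and response. Zero change is one reading; worst score or worst rank would fit the sentence equally well. This stands as far as the value is concerned: the protocol does not prescribe zero change. It does not explain why a rule stated for the efficacy analysis as a whole goes unmentioned in SAP 3.3.

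A second reply is that placebo-based imputation is already cautious. This also stands. On the planning means, the donor rule lowers the expected effect from 1.5 to 1.20 when 20% of the active arm is affected, and it did not raise false positives in the check above.

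A reader might infer three stronger things that the documents do not support:

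- **That these patients are credited with a placebo patient's improvement on every component.** The SAP imputes a donor's Week 8 sub-score, and the change is taken from the patient's own baseline. Symptom scores use the patient's own diary first.
- **That the plan favours the arm with more intolerance.** That is true only relative to a failure score. In absolute terms, more discontinuation makes an effective arm look worse.
- **That the advantage grows with dose.** No document gives discontinuation by dose, and the planning assumption is equal dropout.

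**Conclusion.** The concern holds as an undeclared and untested departure from Protocol 9.2. The SAP has no rule for adverse-reaction discontinuers on the primary MMS change, uses placebo-derived values where a failure score could be expected, and plans no analysis that would show the difference.

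The size is 1.0 x (da - dp) MMS points if failure is scored as zero change and every component comes from a donor, and about one third of that if only endoscopy does. It is nil at the planned equal 5% dropout and small at modest imbalance. It becomes material for power only at imbalances such as 20% versus 5%, which are assumed here. The planned 5% covers dropout for any reason, so adverse reactions would be only part of it. The SAP rule is lenient relative to the protocol's failure rule. It is not a source of false-positive findings in the simulation, which drew donors at random and did not use the SAP's matching score.

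**What to change.** - In SAP 7.3, define treatment failure for the MMS change in patients who discontinue for an adverse reaction before Week 8 and have no Week 8 MMS, for example as no improvement from baseline.
- In SAP 15.1.4, run the primary ANCOVA and the dose comparisons under that rule, at least as a pre-specified sensitivity analysis beside the donor imputation. Which of the two is primary is for the sponsor to decide and justify.
- In SAP 3.3, list the departure from Protocol 9.2 with its reason.

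The cost is a few lines of SAP text and one repeated analysis. Under the failure rule the estimated effect may be slightly smaller. In return, the report would show whether the dose conclusion depends on how intolerance is scored.
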